#### ***Exclusion Criteria***

Subjects are to be excluded from the study if they meet any of the following criteria:

1. Have clinically significant history or evidence of poorly controlled cardiovascular, respiratory, hepatic, renal, gastrointestinal, endocrine, neurological, immunological, or psychiatric disorder(s), or have any other medical condition that, in the Investigator's opinion, would make subjects unsuitable for participation in the study.
2. Have manifest or suspected active COVID-19 infection
  - Have tested positive for presence of SARS-CoV-2 based on a RT-PCR or other validated test, or
  - Have clinical symptoms suggestive of COVID-19 infection, or
  - Have to comply with quarantine requirements per local Public Health directive
3. A history of diagnosis of major depressive disorder in the 3 years prior to Screening, or are on antidepressant, anxiolytic or antipsychotic treatment with the following exception:
  - Selective serotonin reuptake inhibitors (SSRIs) and serotonin and norepinephrine reuptake inhibitors (SNRIs) treatment for mild depression and/or mild anxiety are allowed provided medication is stable and well-tolerated in the 3 months prior to the Screening Visit and does not change during study participation.
  - SSRIs and SNRIs for treatment of VMS are prohibited (see Exclusion Criterion 26)

4. Have a history of suicide ideation or attempt in the past 3 years.
5. Have a sleep disorder other than insomnia due to VMS (eg, narcolepsy, sleep apnea, restless leg syndrome).
6. Have clinical or biochemical evidence of active hepatitis or other significant hepatic or biliary disease (eg, chronic hepatitis, cirrhosis, autoimmune hepatitis, primary biliary cholangitis, primary sclerosing cholangitis, nonalcoholic steatohepatitis, nonalcoholic fatty liver disease, or hereditary liver disease).
7. Have any of the following abnormal laboratory values at Screening:
  - Alanine aminotransferase ( $>1.5 \times$  upper limit of normal [ULN]),
  - Aspartate aminotransferase ( $>1.5 \times$  ULN),
  - Gamma glutamyl transpeptidase ( $>1.5 \times$  ULN),
  - Total bilirubin ( $>1.0 \times$  ULN) (subjects with Gilbert's syndrome can be enrolled if other LFTs are within stated limits),
  - Alkaline phosphatase  $>1.5 \times$  ULN, provided cholestatic or other liver disease is excluded,
  - Estimated glomerular filtration rate (eGFR)  $<60$  mL/min/1.73 m^2 (CKD-EPI 2009 calculation; Levey 2009).

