Abbreviations: ALP = alkaline phosphatase; BP = blood pressure; ECG = electrocardiogram; eDiary = electronic diary; EOS = End of Study; EOT = End of Treatment; ET = Early Termination; E2 = estradiol; FSH = Follicle Stimulating Hormone; HDL-C = high density lipoprotein – cholesterol; HF = hot flash; HFRDIS = Hot Flash Related Daily Interference Scale; HIV = human immunodeficiency virus; INR = international normalized ratio; ISI = Insomnia Severity Index; LDL-C = low density lipoprotein – cholesterol; LFT = liver function test; LH = luteinizing hormone; PK = pharmacokinetic; PT = prothrombin time; SHBG = sex hormone binding globulin; VMS = vasomotor symptoms.

Footnotes are on the following page.

-  Participants who discontinue study treatment and/or the study prior to the scheduled EOT Visit on Day 28 should attend an Early Termination Visit. The procedures at this Early Termination Visit will be the same as those specified for EOT.
-  The Run-In visit may be conducted by phone. During Treatment and Follow-up Period, Day 7, 14, and/or Day 42 (EOS) visits may be conducted either in-clinic or at home.
-  Clinical breast examination will be performed only at Screening. Gynecological examination to be performed at Screening and Day 28 (EOT).
-  Height will be measured at Screening only.
-  Drugs of abuse panel (see [Appendix 4](#)).
-  Vital signs (supine BP and heart rate, and aural body temperature); vital signs should be taken after the subject has been resting for at least 5 minutes. BP assessment for eligibility must be based on the median of a total of 4 to 6 readings, based on 2-3 readings from two different occasions.
-  Total Cholesterol, HDL-C, LDL-C, triglycerides, and fasted glucose will only be collected at Screening and Day 28 (EOT). PT/INR will only be collected at Screening.
-  Testing for presence of virus (SARS-CoV-2) at Screening, Baseline (Day 1), Days 14, 28 (EOT), and 42 (EOS). COVID-19 antibody testing only at Screening, EOT, and EOS.
-  At the discretion of the Sponsor, other analyses including but not limited to hormone assessments may be performed.
-  FSH level to confirm eligibility. All postmenopausal women must have a serum FSH >40 mIU/mL at Screening.

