LIST OF ABBREVIATIONS

| Abbreviation | Full Notations |
|---------------------|---|
| ADL | activities of daily living |
| ADME | absorption, distribution, metabolism and excretion |
| AE | adverse event |
| ALP | alkaline phosphatase |
| ALT | alanine aminotransferase |
| AST | aspartate aminotransferase |
| AUC | area under the concentration-time curve |
| AUC(0-24) | area under the concentration-time curve from time 0 to 24 hours |
| BMI | body mass index |
| BP | blood pressure |
| Cmax | maximum plasma concentration |
| CSR | Clinical study report |
| Ctrough | trough concentration |
| CYP | cytochrome P450 |
| CYP3A4 | cytochrome P450 3A4 |
| DMC | Data Monitoring Committee |
| ECG | Electrocardiogram |
| eCRF | electronic case report form |
| EDC | electronic data capture |
| eDiary | electronic diary |
| eGFR | estimated glomerular filtration rate |
| eITT | exploratory intent-to-treat |
| EOS | End of Study |
| EOT | End of Treatment |
| ePRO | electronic subject reported outcomes |
| ET | Early Termination |
| FSH | follicle-stimulating hormone |
| GCP | Good Clinical Practice |
| GGT | gamma glutamyl transferase |
| GnRH | gonadotropin-releasing hormone |
| HbA1c | glycosylated hemoglobin |
| HBsAg | hepatitis B surface antigen |
| HF | hot flash |
| HFRDIS | Hot Flash Related Daily Interference Scale |
| HT | hormone therapy |
| IB | Investigator Brochure |
| ICF | informed consent form |
| ICH | International Council for Harmonisation |

| | |
|------------------|---|
| IEC | Independent Ethics Committee |
| INR | international normalized ratio |
| IRB | Institutional Review Board |
| IRT | Interactive Response Technology |
| ISI | Insomnia Severity Index |
| ITT | intent-to-treat |
| KNDy | kisspeptin, neurokinin B, and dynorphin |
| LFT | Liver function test |
| LH | luteinizing hormone |
| MEDRA | Medical Dictionary for Regulatory Activities |
| MENQOL | Menopause-Specific Quality of Life |
| MMRM | Mixed effect Model Repeat Measurement |
| MS-VMS | moderate to severe vasomotor symptoms |
| NK3R | neurokinin-3 receptor |
| NKB | neurokinin B |
| OOR | out of range |
| OTC | over the counter |
| PD | pharmacodynamic(s) |
| PGI-C | Subject's Global Impression of Change |
| PK | pharmacokinetic(s) |
| PMW | postmenopausal women |
| PSQI | Pittsburgh Sleep Quality Index |
| QD | once daily |
| QoL | Quality of Life |
| QTcF | QT interval corrected by Fridericia formula |
| RT-PCR | Reverse transcription polymerase chain reaction |

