13. SAFETY ANALYSES

All safety analyses will be based on the safety population defined as all randomized subjects who took at least one dose of study drug, will be descriptive only, and will be presented by treatment group. No inferential testing will be performed. Missing safety data will not be imputed.

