13.3 Clinical Laboratory Evaluation

Laboratory samples will be analyzed by a central laboratory. The central laboratory will provide normal reference ranges for the laboratory results and a flag for all abnormal values.

Laboratory safety parameters for hematology, serum chemistry, and urinalysis will be summarized descriptively at baseline and at each post-baseline time point (Day 14, 28/EOT, and Day 42/EOS) and will include change from baseline. Baseline is defined as the last non-missing value prior to first dose of study drug.

Laboratory safety parameters for liver function tests (LFTs) will be summarized descriptively at baseline and at each post-baseline time point (Day 7, Day 14, 28/EOT, and Day 42/EOS) and will include frequency count and percent for each test category. Potential Hy's Law cases will be identified using the common criteria of 2x upper limit normal (ULN) total bilirubin concurrent with 3x ULN aspartate aminotransferase (AST) or alanine aminotransferase (ALT) (whichever is higher) when aspartate aminotransferase (ALP) is < 2x ULN.

Categorical parameters for urinalysis laboratory results will not be summarized but will be presented in a data listing.

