16. APPENDICES

APPENDIX A: PRESENTATION OF DATA AND PROGRAMMING SPECIFICATIONS

General

- Specialized text styles, such as bold, italics, borders, shading, superscripted and subscripted text will not be used in tables, figures, and data listings unless they add significant value to the table, figure, or data listing.
- Only standard keyboard characters are to be used in tables and data listings.
- Special characters, such as non-printable control characters, printer-specific, or font-specific characters, will not be used on a table, figure, or data listing.
- Hexadecimal character representations are allowed (e.g., μ , a, β).
- All footnotes will be left justified and at the bottom of a page. Footnotes should be used sparingly and must add value to the table, figure, or data listing.

Tables

- Means and medians will be presented to one more decimal place than the raw data. Standard deviations will be presented to two more decimal places than the raw data. Minimums and maximums will be reported with the same number of decimal places as the raw data.
- Percentages will be presented with two decimal places.
- For frequency counts of categorical variables, categories whose counts are zero will be displayed for the sake of completeness. For example, if none of the subjects discontinue due to “lost to follow-up,” this reason will be included in the table with a count of 0. Categories with zero counts will not have zero percentages displayed.
- Percentiles (e.g., 25%, 75%) should be presented to one decimal place more than the raw/derived data.
- The first footnote will be “Source: xxx”, where xxx indicates the source listing number(s) and/or source dataset(s) (e.g., ADaM).

Listings

- If not otherwise specified, all data listings will be sorted by treatment, center, subject number, visit, and date/time as appropriate.
- All date values will be presented in a SAS date (e.g., 29AUG2001) format.
- All observed time values will be presented using a 24-hour clock HH:MM:SS format (e.g., 01:35:45 or 11:26). Seconds will only be reported if they were measured as part of the study.

Standard Calculations

Variables requiring calculation will be derived using the following formulas:

- **Days** – A duration expressed in days between one date (*date1*) and another later date (*date2*) is calculated using the formulas noted below:
duration in days = $date2 - date1 + 1$

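### The potential Hy's Law rule in SAP 13.3 names the wrong analyte for ALP, and its same-sample reading leaves transaminase and bilirubin rises at different draws unflagged

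*SAP*

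**What the plan says.** SAP Section 13.3 has one composite liver rule. It requires twice the upper limit for "total bilirubin concurrent with 3x ULN aspartate aminotransferase (AST) or alanine aminotransferase (ALT"), followed by the condition "whichever is higher) when aspartate aminotransferase (ALP) is < 2x ULN". The multiples 2x and 3x in the first part carry no inequality sign, and *concurrent* is given no sample, visit or day window.

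The same paragraph summarises liver tests at baseline and "at each post-baseline time point (Day 7, Day 14, 28/EOT, and Day 42/EOS").

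The SAP's List of Abbreviations has "ALP | alkaline phosphatase" and lists AST as aspartate aminotransferase. The footnotes to Protocol Table 1 agree: "Abbreviations: ALP = alkaline phosphatase; BP = blood pressure".

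SAP Section 13 makes all safety analyses descriptive: "No inferential testing will be performed". Appendix C plans summary Tables 14.3.6.4 (liver function tests) and 14.3.6.5 (liver function abnormalities), and a chemistry listing, 16.2.8.2.

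**The concern.** A programmer has to code this rule, and its closing condition contradicts itself. Aspartate aminotransferase has already been used in the same sentence, correctly, for AST. Following the words gives a different rule from following the abbreviation.

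The timing matter is separate. If *concurrent* means the same sample, a subject whose ALT or AST passes 3x ULN at one draw, and whose bilirubin passes 2x ULN only at another, is not identified. With efficacy analyses dropped (SAP Section 14), safety is what this SAP analyses, and with few subjects one flag more or less changes the reported count. That makes it worth having a rule that two programmers would code alike, and a simple view of any subject who met both thresholds at different times.

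**Working it through.** The plan states no figure for this rule, so there is none to reproduce. The checks below apply the rule as written. They assume that 2x and 3x mean at or above.

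**1. The analyte.** Inputs: the rule in SAP 13.3 and the two abbreviation lists. Take one sample with bilirubin at or above 2x ULN. Band AST as <2, 2 to <3, or ≥3; ALT as <3 or ≥3; alkaline phosphatase as <2 or ≥2. That gives 3 × 2 × 2 = 12 patterns. In 4 of them neither transaminase reaches 3x, and neither coding flags them. The other 8 are:

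| AST | ALT | Alk. phos. <2: by abbreviation / by words | Alk. phos. ≥2: by abbreviation / by words |
|---|---|---|---|
| <2 | ≥3 | yes / yes | no / yes |
| 2 to <3 | ≥3 | yes / no | no / no |
| ≥3 | <3 | yes / no | no / no |
| ≥3 | ≥3 | yes / no | no / no |

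- By the abbreviation (AST or ALT ≥3, alkaline phosphatase <2): 4 flagged.
- By the words (AST or ALT ≥3, AST <2): 2 flagged. AST cannot be both ≥3 and <2, so the AST route is void and only ALT ≥3 with AST <2 remains.
- Flagged by both: 1. Missed by the words: 4 − 1 = 3. Wrongly flagged by the words: 2 − 1 = 1 (AST <2, ALT ≥3, alkaline phosphatase ≥2).

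These are unweighted patterns, not proportions of subjects.

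**2. The timing.** Inputs: four planned post-baseline liver draws, Days 7, 14, 28 and 42 (SAP 13.3). Suppose each rise is seen at exactly one draw.

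- Pairings of transaminase draw and bilirubin draw: 4 × 4 = 16.
- Same draw, flagged: 4.
- Bilirubin later: 6, of which 3 are at the very next draw. Bilirubin earlier: 6. Total not flagged: 16 − 4 = 12.
- A screen on each subject's maximum values, without the alkaline phosphatase condition, flags all 16.

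Example: AST 5x and ALT 6x on Day 14, both below 3x by Day 28, bilirubin 1.2x on Day 14 and 2.5x on Day 28, alkaline phosphatase 1x throughout. The same-sample rule, correctly coded, does not flag this subject; the maximum-value screen does. The profile is invented for illustration.

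**3. Distance between draws.** From the visit windows in Protocol Table 1 (7±2, 14±2, 28±3, 42±3):

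- Day 7 to 14: 12 − 9 = 3 to 16 − 5 = 11 days.
- Day 14 to 28: 25 − 16 = 9 to 31 − 12 = 19 days.
- Day 28 to 42: 39 − 31 = 8 to 45 − 25 = 20 days.

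**4. Same sample or same visit.** SAP Section 7 maps Days 15 to 28 to Day 28/EOT and Days 29 to 42 to Day 42/EOS. If those ranges assign samples to visits, a same-visit rule could pair samples up to 28 − 15 = 13 days apart (likewise 42 − 29 = 13). The two readings can differ, so the definition should say sample.

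**The case against.** The strongest reply is that the analyte slip corrects itself. The abbreviation is right, both lists confirm it, and the rule says that it follows the common criteria. A competent programmer would code alkaline phosphatase and lose nothing. That stands, and literal coding is the less likely outcome. The sentence is still an operative derivation, and SAP Appendix B asks for programs to be checked against SAP derivation rules, so it should be corrected.

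On timing, *concurrent* ordinarily means at the same time, the recommendation keeps that meaning, and nothing in the supplied documents requires a wider screen. This also stands: the missing definition is a lack of detail, and the wider screen is a low-cost addition, not the repair of an error.

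The 4-of-16 count invites the inference that the rule would miss three quarters of cases. The documents do not support that. The count gives each pairing equal weight and assumes that each rise appears at one draw only; rises that persist can overlap and be flagged. It also assumes four draws per subject. SAP Section 14 says that all subjects were withdrawn when the study was terminated, and early leavers were due an Early Termination visit, so many may have fewer draws at other spacings.

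Finally, other safeguards may exist. The content of Table 14.3.6.5 is not specified, the events of special interest are not defined in the supplied text, only the protocol synopsis and schedule are available, and the DMC in SAP 10.2 includes hepatology expertise. The claim is therefore only that the supplied SAP text describes no other pairing screen.

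**Conclusion.** The point holds and is minor. The closing condition of the rule is wrong as worded. Its intent is recoverable, and coding that intent causes no misses; coding the words would void the AST route and ignore alkaline phosphatase. Read as same-sample, the rule does not flag subjects who cross the two thresholds only at different draws.

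The effect is small. The safety analysis is descriptive and few subjects were randomized. Individual values can be reviewed by hand in listing 16.2.8.2, since "all data listings will be sorted by treatment, center, subject number, visit, and date/time as appropriate"; this assumes that the listing holds all the liver tests, including the Day 7 draw. Tables 14.3.6.4 and 14.3.6.5 are summaries by title and cannot be relied on for individual profiles.

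The number of subjects affected cannot be estimated. SAP 13.1 records termination for safety reasons, and a reader might infer that liver events were the cause or that a case was overlooked. The documents do not give the reason and report no liver results, so neither inference is supported.

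**What to change.** In SAP Section 13.3:

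1. Replace the spelled-out term in the closing condition with alkaline phosphatase (ALP).
2. State that *concurrent* means the same sample, and that 2x and 3x mean at or above.
3. Keep that rule and add a supplementary descriptive screen without the ALP condition. It flags any subject whose maximum post-baseline ALT or AST reaches 3x ULN and whose maximum post-baseline total bilirubin reaches 2x ULN, at any time. Use all post-baseline samples, including early-termination and unscheduled ones. Show the dates of both elevations and the ALP values for review, for example alongside Table 14.3.6.5.

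The cost is one corrected term, a short definition and one derivation from data already collected. It needs a short change to Section 13.3: the allowance in Appendix C for minor changes without amendment covers only the index of outputs. The downside is a few non-specific flags. Subjects with Gilbert's syndrome are an example, because Protocol Exclusion Criterion 7 lets them in with raised bilirubin ("syndrome can be enrolled if other LFTs are within stated limits"); subjects with high alkaline phosphatase are another. The dates and ALP values are shown so that a reviewer can set such cases aside.

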13.4 Electrocardiogram

Descriptive statistics at baseline and end of treatment (Day 28) as well as changes from baseline will be summarized for each electrocardiogram (ECG) parameter. Baseline is defined as the last non-missing value prior to first dose of study drug.

13.5 Vital Signs

Vital signs will be summarized using descriptive statistics at baseline and at each post-baseline time point (Day 7, 14, 28/EOT, 42/EOS) and will include change from baseline. Baseline is defined as the last non-missing value prior to first dose of study drug.

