#### Safety

- Incidence and severity of AEs and serious AEs for SJX-653.
- Change from Baseline to worst (parameter dependent) and last values in vital sign parameters.
- Change from Baseline in clinical laboratory values.
- Change from Baseline in physical examination and ECG.

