6. GENERAL ANALYSIS CONSIDERATIONS

The statistical analyses will be reported using summary tables, listings, and figures (TLFs). The International Council for Harmonisation (ICH) numbering convention will be used for all TLFs.

Continuous variables will be summarized with means, standard deviations, medians, minimums, and maximums. Other summaries (e.g., 95% confidence intervals) may be used as appropriate and will be mentioned in the respective sections.

Categorical variables will be summarized by counts and by percentage of subjects in corresponding categories. Percentages for missing values are omitted and do not account for the percent calculation of other categories. Percentages are routinely based on the total category count excluding the missing category if not otherwise mentioned. Percentages showing a rate relative to the total number of subjects in this group are given in special tables (e.g., adverse event [AE] tables). Footnotes will specify the percent basis in those cases.

All summary tables will be presented by treatment group and will also include a total column.

Individual subject data obtained from the eSource forms and external vendors (e.g., central clinical laboratory) will be presented in data listings as identified in Sections 9 and 13.

The analyses described in this plan are considered a priori, in that they have been defined prior to breaking the blind.

Any analyses performed subsequent to breaking the blind will be considered post hoc and exploratory. Post hoc analyses will be labeled as such on the output and identified in the CSR.

All analyses and tabulations will be performed using SAS® software Version 9.4 or higher unless otherwise noted. Tables and listings will be presented in RTF format. Upon completion, all SAS® programs will be validated by an independent programmer. In addition, all program output will undergo a senior level statistical review. The validation process will be used to confirm that statistically valid methods have been implemented and that all data manipulations and calculations are accurate. Checks will be made to ensure accuracy, consistency with this plan, consistency within tables, and consistency between tables and corresponding data listings. Upon completion of validation and quality review procedures, all documentation will be collected and filed by the project statistician or designee.

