13.2 Adverse Events

All AE summaries will be restricted to treatment-emergent AEs (TEAEs), which are defined as those AEs that occurred after dosing and those existing AEs that worsened after start of dosing. If it cannot be determined whether the AE is treatment-emergent due to a partial onset date, then it will be counted as such. Verbatim terms in the eSource forms will be mapped to preferred terms and system organ classes using the Medical Dictionary for Regulatory Activities (MedDRA) (version 23.0).

Each AE summary will be displayed by treatment group. Summaries that are displayed by system organ class and preferred terms will be ordered by descending subject count in the total column by system organ class and preferred term. Summaries of the following types will be presented:

- Overall summary of TEAEs.
- Subject incidence of TEAEs and total number of unique TEAEs by MedDRA system organ class and preferred term.
- Subject incidence of TEAEs of special interest and total number of unique TEAEs by MedDRA system organ class and preferred term.
- Subject incidence of treatment-related TEAEs and total number of unique TEAEs by MedDRA system organ class and preferred term.
- Subject incidence of serious TEAEs and total number of unique serious TEAEs by MedDRA system organ class and preferred term.

- Subject incidence of TEAEs leading to study discontinuation and total number of unique TEAEs leading to study discontinuation by MedDRA system organ class and preferred term.

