13.6 Physical Examination

Physical examination results will be listed.

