APPENDIX C: LIST OF TABLES, LISTINGS, AND FIGURES

The following proposal for section 14 and 16.2 is completed according to ICH E3 guidelines. The ICH heading numbers and description are in **bold**. Minor changes from this planned index do not need to be amended in the SAP.

TABLES, FIGURES AND LISTINGS

Index of Section 14

| Table Number | Table Title | Analysis Set |
|---------------|--|-------------------|
| 14 | Tables and Figures Referred to but not Included in the Text | |
| 14.1 | Demographic Data | |
| 14.1.1 | Subject Disposition | |
| 14.1.2 | Summary of Demographic and Baseline Characteristics | Safety Population |
| 14.1.3 | Summary of Protocol Deviations Due to COVID-19 | Safety Population |
| 14.3 | Safety Data | |
| 14.3.1 | Displays of Adverse Events | |
| 14.3.1.1 | Overall Summary of Treatment-Emergent Adverse Events | Safety Population |
| 14.3.1.2 | Treatment-emergent Adverse Events by System Organ Class and Preferred Term in Descending Frequency | Safety Population |
| 14.3.1.3 | Treatment-emergent Adverse Events of Special Interest by System Organ Class and Preferred Term in Descending Frequency | Safety Population |
| 14.3.1.4 | Treatment-emergent Treatment-related Adverse Events by System Organ Class and Preferred Term in Descending Frequency | Safety Population |
| 14.3.1.5 | Serious Adverse Event by System Organ Class and Preferred Term | Safety Population |
| 14.3.1.6 | Treatment-emergent Adverse Event Leading to Study Discontinuation by System Organ Class and Preferred Term | Safety Population |
| 14.3.5 | Extent of Exposure | |
| 14.3.5 | Summary of Study Drug Exposure | Safety Population |
| 14.3.6 | Other Safety Data | |
| 14.3.6.1 | Observed Values and Change from Baseline in Clinical Laboratory Parameters, Hematology | Safety Population |

| Table Number | Table Title | Analysis Set |
|--------------|--|-------------------|
| 14.3.6.2 | Observed Values and Change from Baseline in Clinical Laboratory Parameters, Chemistry | Safety Population |
| 14.3.6.3 | Observed Values and Change from Baseline in Clinical Laboratory Parameters, Urinalysis | Safety Population |
| 14.3.6.4 | Observed Value and Change from Baseline in Clinical Laboratory, Liver Function Tests | Safety Population |
| 14.3.6.5 | Liver Function Abnormalities | Safety Population |
| 14.3.7 | Observed Values and Change from Baseline in ECG Tests | Safety Population |
| 14.3.8 | Observed Values and Change from Baseline in Vital Signs | Safety Population |

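### The SAP specifies no per-subject worst or last vital-sign summary and no AE summary by severity, although both are protocol safety endpoints, and SAP Section 14 does not name them as dropped

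*SAP*

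**What the plan says.** **Protocol synopsis, Secondary Endpoints, Safety.** Three of the four bullets matter here: "Change from Baseline to worst (parameter dependent) and last values in vital sign parameters"; "Incidence and severity of AEs and serious AEs for SJX-653"; and "Change from Baseline in physical examination and ECG".

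**SAP 13.5 and Appendix C.** The vital-sign text reads "Vital signs will be summarized using descriptive statistics at baseline and at each post-baseline time point (Day 7, 14, 28/EOT, 42/EOS"), with change from baseline. The one matching table, 14.3.8, is titled "Observed Values and Change from Baseline in Vital Signs". SAP Section 6 adds that "Continuous variables will be summarized with means, standard deviations, medians, minimums, and maximums".

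**SAP 13.2.** Six kinds of summary are planned: overall, all treatment-emergent AEs (TEAEs), special interest, treatment-related, serious, and leading to study discontinuation. The first appears only as "Overall summary of TEAEs", with no account of its rows.

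**SAP 13.4 and 13.6.** ECG parameters are summarized at baseline and at end of treatment, which 13.4 equates with Day 28. For the other half of the protocol bullet, "Physical examination results will be listed".

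**SAP Section 14.** Because few subjects were randomized, only a selection of the safety data will be summarized, as Section 13 sets out. Efficacy is expressly dropped. No individual safety endpoint is named as dropped.

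**The concern.** A protocol endpoint should either have an analysis in the SAP or be named as no longer analysed. Several safety endpoints here have neither.

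The safety tables are this study's main remaining output. SAP 13.1 records that sites were told on 12 February 2021 that the study was terminated for safety reasons. Efficacy will not be tabulated and PK will not be summarized.

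Two safeguards in the SAP do not reach the gap. The Introduction promises that the CSR will document deviations from the SAP, but an endpoint that the SAP leaves out is not a deviation from it. Section 6 treats any analysis carried out after unblinding as post hoc and exploratory, so a protocol endpoint restored late would carry that label.

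A smaller, related point concerns subjects withdrawn before Day 28. The SAP does not say that an early termination (ET) ECG belongs in the only post-baseline ECG row of 13.4.

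**Working it through.** The plan states no figure on this point, so the check is a comparison of texts, a count of tables, and a look at what by-visit statistics can and cannot show.

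**1. Endpoints against the SAP.** Protocol bullets are split only for layout.

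| Protocol safety endpoint | SAP Section 13 | Appendix C table | Named as dropped in Section 14 |
|---|---|---|---|
| AE/SAE incidence | 13.2 | 14.3.1.1 to 14.3.1.6 | not needed |
| AE/SAE severity | not specified (overall summary undefined) | none by title | no |
| Vital signs, change to worst | not specified | none by title | no |
| Vital signs, change to last | not specified | none by title | no |
| Laboratory change | 13.3 | 14.3.6.1 to 14.3.6.5 | not needed |
| Physical examination change | 13.6, listing only | none | no |
| ECG change | 13.4 | 14.3.7 | not needed |

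**2. Table count.** 14.1.1 to 14.1.3 (3) + 14.3.1.1 to 14.3.1.6 (6) + 14.3.5 (1) + 14.3.6.1 to 14.3.6.5 (5) + 14.3.7 and 14.3.8 (2) = 17. By title, 0 of 17 is a worst-value, last-value or severity summary.

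**3. Do by-visit minimums and maximums stand in for worst and last?** Let D(i,j) be subject i's change from baseline at visit j. Table 14.3.8 gives, for each j, statistics over subjects i. For a parameter whose worst direction is upward, the endpoint is W(i) = the maximum over j of D(i,j), summarized over i.

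- The largest W(i) in an arm is the largest of the by-visit maximums of change, so the single extreme can be recovered.
- The mean, SD and median of W(i) cannot, because subjects reach their worst values at different visits.
- The last value is D(i,j) at subject i's own final visit. In a trial where all subjects were withdrawn at termination, those visits differ. No single row holds every subject's last value, although a worst or last row would keep every subject with any post-baseline measurement.

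**4. Where does an ET ECG go?** SAP Sections 7 and 13 contain no ET rule. Two sources bear on it.

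- The day ranges in SAP Section 7, taken literally, label Days 2 to 7 as Day 7, Days 8 to 14 as Day 14, Days 15 to 28 as Day 28/EOT, and Days 29 to 42 as Day 42/EOS. An ET ECG on Days 2 to 14 would then fall where 13.4 has no row.
- Protocol Table 1 has one shared column for end of treatment and early termination, and its first footnote gives both visits the same procedures. That places the ECG with EOT.

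As a test, the Section 7 ranges can be applied to visits inside the protocol windows:

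- Day 7 + 2 = 9, so a visit on Days 8 to 9 would be called Day 14.
- Day 14 + 2 = 16, so a visit on Days 15 to 16 would be called Day 28/EOT.
- Day 28 + 3 = 31, so an EOT visit on Days 29 to 31 would be called Day 42/EOS.

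Used as analysis windows, the ranges misplace visits that are on schedule. They stand under a heading about visit terminology and are better read as labels. The better reading is that an ET ECG belongs with EOT.

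**The case against.** **The reduction is disclosed.** Section 14 is the right place, gives a reason and points to Section 13. This stands against any inference that the SAP hides the change. It does not supply the names of the dropped endpoints, which Section 14 does supply for efficacy.

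**Severity may be in the overall summary.** The rows of Table 14.3.1.1 are not described, and the SAP refers to mock tables that are not part of the documents. This stands. A reader might infer that the SAP abandons AE severity, but the documents support only that no severity summary is specified.

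**Last values are largely covered.** For a subject who reaches Day 42, her last scheduled value is in the Day 42/EOS row. If ET maps to EOT, an early withdrawal's ET value is in the 28/EOT row. This stands in part: the values appear, but spread over rows and not as one by-arm summary.

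**Counting failures.** From the table above a reader might conclude that most of the protocol's safety endpoints go unanalysed. That count depends on how four bullets are split, and it would treat physical examination as a failure although 13.6 lists it.

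**ECGs lost to the day ranges.** A reader might infer that ECGs of subjects withdrawn early would be left out of the table. That requires the Section 7 labels to be analysis windows, which the on-schedule visits argue against. SAP Section 5 also pairs Week 4 with ET, though only in describing the sample-size SD. What remains is a request for one clarifying label.

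**Little is at stake.** The analysis is descriptive, without testing, and AEs, vital signs, ECGs and physical examinations are listed by subject. This stands, and it limits the weight of the point.

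**Conclusion.** The concern holds in a limited form. Two protocol safety endpoints, change to worst and last vital-sign values and AE severity, have no specified summary in SAP Section 13 or Appendix C. Change in physical examination is listed only. Section 14 names none of these.

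The loss is of by-arm, per-subject summaries. It is not a loss of data, and no efficacy inference is involved. A reader might infer from the safety stop that vital signs or ECG findings prompted it; the documents do not say so.

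The conclusion rests on the SAP text and on table titles, since no table shells are available. A severity breakdown inside Table 14.3.1.1 would close that part. The documents give neither the number of subjects randomized by the time of termination nor the number with an ET visit, so the number affected cannot be stated.

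**What to change.** - **13.5:** add, by arm, change from baseline to each subject's worst post-baseline value, with the direction of worst stated for each parameter, and to her last post-baseline value. Run both through the last visit, because the protocol endpoint sets no cut-off. Any row restricted to EOT/ET should be additional and labelled as such.
- **13.2:** add TEAEs and serious TEAEs by maximum severity.
- **13.4:** label the post-baseline row as Day 28/EOT or ET, in line with the protocol's shared column, so that ECGs of subjects withdrawn early are counted. Footnote the study day or the days since last dose. Do not call the row on-treatment, since an ET visit may follow the stop of dosing.
- **Section 14:** name every protocol safety endpoint still not summarized, including change in physical examination if it stays listed only.

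**Cost.** A few more descriptive tables or rows from data already collected, and short text edits. There are no new assessments. The Appendix C allowance for minor changes without amendment covers the table index only, so the edits to Sections 13 and 14 need a SAP revision. The combined ECG row pools different study days, which is why it needs the footnote. Subjects with no post-baseline measurement still contribute nothing.
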